8. ASSESSMENT OF SAFETY

8.1. Safety Parameters

Safety will be characterized in terms of the incidence, timing, severity (graded by the National Cancer Institute [NCI] Common Terminology Criteria for Adverse Events [CTCAE], Version 4.0), seriousness, and relatedness of adverse events and laboratory abnormalities. In addition, physical examination, vital signs, and ECOG performance status will be serially monitored. Laboratory safety analyses will be based on the local laboratory data, and will include hematology, serum chemistry (including liver and kidney function), urinalysis, serum or urine pregnancy testing, and coagulation profile. Serum will also be assessed for immunogenicity to TRC105 (APA titers). In addition, ECGs will be recorded at baseline and day 1 of each cycle and as clinically indicated throughout the study.

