A hazard ratio (HR) of 0.67 is considered to be clinically relevant. Based on 1:1 randomization and the use of a one-sided log-rank test at the $\alpha=0.10$ level of significance, 115 events are required in order to have 80% power to detect a HR of 0.67. The expected PFS of patients treated with axitinib who have progressed following first line treatment with a VEGFR TKI is 4.8 months. Based on a planned accrual period of 12 months, and a minimum follow-up period of 4.3 months, approximately 150 patients will be required. Timing of the final analysis of PFS will be determined by the sponsor based on the expected total number of events that define PFS and the timing of these events, and may occur prior to the occurrence of 115 events.

5. Analysis Population

The safety population includes all patients who receive at least a portion of one dose of the study drug, TRC105 or axitinib (phase 2 portion).

The phase 2 study population for efficacy will include all randomized patients (intention to treat).

The Phase 1b study population for efficacy will include all patients who receive treatment with axitinib and TRC105.

6. General Analysis Comments

Summary statistics will include frequencies and percents of responses in each category for discrete measures; and may include means, medians, standard deviations, minimum and maximum values for continuous measures. Listings of data represented on the Case Report Form (CRF) will be provided.

SAS[®], Version 9.0 or higher or R version 2.15 or higher, will be used to perform all statistical analyses.

7. Missing Data

All data collected, including unscheduled visits, will be presented in the data listings. Summary tables will generally be limited to planned visits.

In all analyses, except for partial dates, it is expected that only observed values will be presented; no imputation of missing data will be conducted. Partial dates will be imputed according to the following table. CRFs that are not listed below are not expected to contain partial dates. CRF versions may change. Only if a change impacts the imputation of a partial date will the SAP be amended.

Planned Imputation Methods for Partial Dates

CRF	Field	Planned Imputation Method	
		Month and Year Given	Year Given
Adverse Events	Date of Onset	First of Month	Jan 01 of Year
	Date of Resolution	Last day of Month	Dec 31 of Year
Concomitant Medications	Start Date	First of Month	Jan 01 of Year
	Stop Date	Last day of Month	Dec 31 of Year

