12.3. Laboratory Evaluations

Quantitative laboratory test results and changes from baseline will be summarized at each visit for hematology, coagulation, serum chemistry panel, and urinalysis.

The Investigator will determine whether abnormal lab values are clinically significant. Such results are to be reported as adverse events and CTCAE grading will be assigned (except for urinalysis) where applicable.

Laboratory results that are abnormal and clinically significant will be flagged by the investigator. Abnormal and clinically significant results will be presented in listings with Investigator comments.

The number and percentage of patients who exhibit clinically significant abnormal laboratory results will be produced at each visit.

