 - 14.3.1.8. Number (%) of Patients with Adverse Events Leading to Discontinuation
 - 14.3.2. Listings of Deaths, Other Serious and Significant Adverse Events
 - 14.3.3. Narratives of Deaths, Other Serious and Certain Other Significant Adverse Events
 - 14.3.3.1 Narratives of Deaths
 - 14.3.3.2 Narratives of Serious Unexpected Related Adverse Events
 - 14.3.4. Abnormal Laboratory Value Listing (Each Patient)
 - 14.3.4.1. Clinical Laboratory Results - Hematology: Change from Baseline
 - 14.3.4.2. Clinical Laboratory Results – Coagulation: Change from Baseline

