14.3.3.1 Narratives of Deaths

14.3.3.2 Narratives of Serious Unexpected Related Adverse Events

14.3.4. Abnormal Laboratory Value Listing (Each Patient)

20. Appendix 2 Listings

20.1. Appended Listings Phase 1b (by dose cohort):

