- Listing 16.2.6.5 SPD (target lesions) over time compared to baseline
- Listing 16.2.6.6 Non-Target Lesions
- 16.2.7 Adverse Event Listings (Each Patient)
 - Listing 16.2.7.1 All Adverse Events
 - Listing 16.2.7.2 Serious Adverse Events
 - Listing 16.2.7.3 Adverse Events Leading to Discontinuation
 - Listing 16.2.7.4 Adverse Events with an Outcome of Death
 - Listing 16.2.7.5 Disposition (including Adverse Events) of Patients with a Serious or TRC105 related Adverse Event at Withdrawal
- 16.2.8 Individual Laboratory Measurements by Patient
 - Listing 16.2.8.1 Abnormal Laboratory Results – Hematology
 - Listing 16.2.8.2 Abnormal Laboratory Results – Coagulation
 - Listing 16.2.8.3 Abnormal Laboratory Results – Chemistry
 - Listing 16.2.8.4 Abnormal Laboratory Results – Urinalysis
 - 16.2.8.5 Final Immunogenicity Report
- 16.2.9 Other
 - Listing 16.2.9.1 Vital Signs
 - Listing 16.2.9.2 Abnormal and Clinically Significant Physical Exam Results
 - Listing 16.2.9.3 ECG Results
 - Listing 16.2.9.4 ECOG Performance Status
 - Listing 16.2.9.5 Pregnancy at Screening
 - Listing 16.2.9.6 Archival Tumor Specimen
 - Listing 16.2.9.7 Drug allergies
 - Listing 16.2.9.8 Protein Biomarkers

20.3. Figures Phase 2:

- 14.2.1 Kaplan Meier Survival Plot of PFS by arm
- 14.2.2 Kaplan Meier Survival Plot of PFS by arm where TGF β receptor III > median
- 14.2.3 Kaplan Meier Survival Plot of PFS by arm where TGF β receptor III < median
- 14.2.4 Kaplan Meier Survival Plot of PFS by arm where osteopontin > median
- 14.2.5 Kaplan Meier Survival Plot of PFS by arm where osteopontin < median
- 14.3.4.1 Clinical Laboratory Results – Hematology by arm over time (hemoglobin, white blood cell count, platelets)
- 14.3.4.2 Clinical Laboratory Results – Coagulation by arm over time (PT, INR)
- 14.3.4.3 Clinical Laboratory Results – Chemistry by arm over time (AST, ALT, Alk Phos, t bili, BUN, creatinine, calcium, phosphorus, glucose, lipase, TSH, amylase, sodium, potassium, chloride and bicarbonate)

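### Per-patient laboratory severity by arm rests on investigator-flagged adverse events; one worst-grade and shift table using unscheduled values would be a cheap addition

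*SAP*

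**What the plan says.** Protocol 8.1 describes safety by incidence, timing, CTCAE severity, "seriousness, and relatedness of adverse events and laboratory abnormalities". For the laboratory analysis itself, Protocol 10.5.2 plans summaries of baseline, treatment visits and change from baseline for each arm.

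The SAP carries that out by visit:

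- SAP 7 (Missing Data): all data, unscheduled visits included, go into listings, but "Summary tables will generally be limited to planned visits".
- SAP 12.3: "Quantitative laboratory test results and changes from baseline will be summarized at each visit for hematology, coagulation, serum chemistry panel, and urinalysis". It adds: "The number and percentage of patients who exhibit clinically significant abnormal laboratory results will be produced at each visit".
- SAP 6: summary statistics "may include means, medians, standard deviations, minimum and maximum values for continuous measures".
- SAP 19.2 names Phase 1b laboratory tables such as "Hematology: Change from Baseline". For Phase 2, SAP 19.4 names "14.3.4. Abnormal Laboratory Value Listing (Each Patient)" and SAP 20.3 names figures such as "Hematology by arm over time (hemoglobin, white blood cell count, platelets)". SAP 20.2 adds listings of abnormal results.

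No output named in SAP 19 or 20 is a worst post-baseline table, a shift table, or a table of CTCAE grades derived from laboratory values.

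**The concern.** By-visit laboratory summaries do not add up to per-patient incidence. The same patient can be counted at several visits, so counts at each visit cannot be summed into the number of patients ever affected. A by-visit mean also misses a nadir that falls between planned visits. The minimum and maximum in SAP 6 are optional, and they give the group extreme at one visit, not each patient's worst value.

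Unscheduled bloods are to be expected. Protocol 8.1.1.1 allows extra tests for treatment planning or for following adverse events, and footnote 8 of Table 10 asks for further assessment as needed for safe treatment. Such samples are often drawn when a patient is unwell, yet they are generally kept out of the summaries.

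The toxicity most affected is the one already known. Protocol 2.3.2.1 names anemia as the dose-limiting toxicity of single-agent TRC105. It also reports clinically significant anemia in 9 of 19 patients given 10 mg/kg with bevacizumab, six of them grade 3. Protocol 2.3.6.1 asks for close monitoring. A comparison by arm of how far each patient's hemoglobin fell is an obvious display for this drug, and the plan does not name one.

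**Working it through.** The plan gives no figure to reproduce. The check has two parts: which laboratory values reach which output, and how a worst-value table would behave under the planned sampling.

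**1. Where a Phase 2 laboratory value ends up**

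| Value | By-visit summary or figure | Per-patient summary by arm |
|---|---|---|
| Scheduled, reported as an AE | Yes | Yes, through AE tables |
| Scheduled, not reported as an AE | Yes, but without its grade | No; individual value in listings |
| Unscheduled, reported as an AE | Generally no (SAP 7) | Yes, through AE tables |
| Unscheduled, not reported as an AE | Generally no (SAP 7) | No; listings only |

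The routes into the AE tables are:

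- a clinically significant result (Protocol 8.1.1, SAP 12.3);
- one of the triggers in Protocol 8.2.1, including investigator or sponsor judgment;
- a Hy's Law case (Protocol 8.2.2);
- a grade change in an existing AE (Protocol 8.3.9).

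These AEs are counted per patient and by arm (SAP 12.2) and enter Table 14.3.1.4, which gives the maximum CTCAE grade (SAP 19.4). The entry threshold is judgment. Under Protocol 8.1.1, clinical significance generally means a change in management, not a CTCAE cut-off. Protocol 2.3.3 describes the trial as open label.

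**2. Planned post-baseline samples through k cycles (k at least 2, End of Study visit excluded)**

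- Hematology, Arm A (Table 9): C1D15, C2D1, C2D15, then day 1 of cycles 3 to k. Total 3 + (k − 2) = k + 1.
- Hematology, Arm B (Table 10; same days in Table 11): C1D15, then days 1 and 15 of cycles 2 to k. Total 1 + 2(k − 1) = 2k − 1.
- Hematology on days planned in both arms: k + 1 in each.
- Chemistry: k + 1 in both arms.

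| Cycles | Arm A hematology | Arm B hematology |
|---|---|---|
| 4 | 5 | 7 |
| 6 | 7 | 11 |
| 12 | 13 | 23 |

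**3. What unequal sampling could do to a worst-grade table when there is no true difference**

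Assume each sample independently has the same chance p of showing a given grade in both arms. Then P(at least one) = 1 − (1 − p)^n. At six cycles (n = 7 and 11):

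| p | Arm A | Arm B |
|---|---|---|
| 1% | 1 − 0.99^7 = 6.8% | 1 − 0.99^11 = 10.5% |
| 2% | 1 − 0.98^7 = 13.2% | 1 − 0.98^11 = 19.9% |
| 5% | 1 − 0.95^7 = 30.2% | 1 − 0.95^11 = 43.1% |

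Results within a patient are correlated, which shrinks these gaps toward zero. On days planned in both arms each arm has 7 samples at six cycles, and the artefact from planned sampling disappears. These figures size the side effect of the remedy. They do not size the present gap, for which the documents give no input.

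**The case against.** A reader might infer that the SAP contradicts Protocol 8.1, or that the incidence and severity of laboratory abnormalities are not summarized per patient at all. The documents support neither reading. Protocol 8.1 specifies no table, and the protocol's own analysis section, 10.5.2, asks for by-visit laboratory summaries, which SAP 12.2 and 12.3 follow. The sentence in 8.1 also lists seriousness and relatedness, which the protocol defines for adverse events, so the AE route is a natural way to deliver it. For flagged abnormalities, incidence by arm and maximum grade are both planned.

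Nor should the absence of change-from-baseline laboratory tables from the Phase 2 output list be read as dropping them. SAP 12.2 and 12.3 commit to those summaries in the text, and the Phase 2 figures cover hemoglobin, platelets, AST, ALT and creatinine by arm.

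The anemia argument can be pressed too far. Protocol 2.3.1.3 describes a hypoproliferative anemia linked to drug accumulation: grade 3 in cycle 2, with one patient reaching grade 4 in cycle 3. That suggests a gradual fall, and Arm B hematology is planned about every two weeks. A fall that prompts transfusion or dose reduction is a change in management and should become a graded AE. SAP 7 also says only that tables are generally limited to planned visits, which leaves some discretion.

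All of this stands, and it sets the priority. It does not remove the dependence on flagging: where nobody reports a graded value as an AE, no per-patient table by arm shows its grade.

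**Conclusion.** The point holds as a cheap improvement of optional to moderate priority. Per-patient laboratory incidence and severity by arm are summarized only for abnormalities that investigators or the sponsor report as AEs, and investigators make that call knowing the arm. Other graded values and unscheduled values generally have to be found in listings.

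The size of the gap cannot be estimated, because the documents do not give the number of unscheduled samples or the share of graded values that go unreported. The primary PFS analysis and the AE tables are unaffected. The conclusion rests on reading SAP 7 as it would normally be applied, and on the output lists in SAP 19 and 20 being complete.

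**What to change.** Keep the by-visit tables on planned visits. Amend SAP 7 and 12.3 to add one Phase 2 table by arm giving each patient's worst post-baseline CTCAE laboratory grade and the shift from baseline. Use all scheduled and unscheduled values from first dose to 28 days after last dose, which matches the treatment-emergent window in SAP 12.2. Where local reference ranges are unavailable, show worst value and change from baseline instead of grade.

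Footnote that from cycle 3 hematology is planned on day 1 in Arm A but on days 1 and 15 in Arm B, and that unscheduled sampling is discretionary. Beside the table, show a hematology version restricted to days planned in both arms (C1D15, C2D1, C2D15, then day 1 of each later cycle). That version removes the lean against TRC105 but also drops the unscheduled values, so the two need to be read together.

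The cost is SAP wording, one table shell with its sensitivity version, and a grade derivation. Whether reference ranges are in the database is not stated. No new data are collected, so gaps in collection remain: Tables 9 to 11 plan no hematology or chemistry at the 28-day follow-up and no INR after cycle 2 day 1.

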Concomitant Treatment	Start Date	First of Month	Jan 01 of Year
	Stop Date	Last day of Month	Dec 31 of Year
Informed Consent Reconsent	Date of Consent/Reconsent	Last day of Month	Dec 31 of Year
Medical History and Baseline Emergent AE	Start Date	First of Month	Jan 01 of Year
	Stop Date	Last day of Month	Dec 31 of Year
Primary Diagnosis	Date of Diagnosis	Last day of Month	Dec 31 of Year
Prior Cancer Surgery	Date of Surgery	Last day of Month	Dec 31 of Year
Prior Cancer Therapy	Start Date	First of Month	Jan 01 of Year
	Stop Date	Last day of Month	Dec 31 of Year
	Date of Progression on Therapy	Last day of Month	Dec 31 of Year
Prior Radiation Therapy	Start Date	First of Month	Jan 01 of Year
	Stop Date	Last day of Month	Dec 31 of Year
Demography	Birth Date	15 th of the Month	Jun 15 of Year

8. Patient Accountability and Patient Disposition

The number enrolled, the number of doses received and the number of cycles completed (per Section 12.1) will be presented for each dose level for the phase 1 portion and by treatment group for the phase 2 portion. A summary of reasons for withdrawal will be provided. The number of patients in the safety populations will also be presented. Patient disposition, including reasons for discontinuation, and number of cycles completed will be listed.

9. Demographics and Baseline Characteristics

Demographics and baseline characteristics will be summarized by dose level. Demographic variables, including age, gender, and race will be summarized in a tabular form.

Initial diagnosis, prior cancer surgery, prior radiotherapy, prior cancer therapy, and medical history will be listed. Initial diagnosis, prior cancer surgery, prior radiotherapy, and prior cancer therapy will also be summarized by dose level for the phase 1 portion and by treatment group for the phase 2 portion.

10. Concomitant Medications and Treatments

A listing of all concomitant medications and treatment will be provided by patient, drug name, start and stop dates, whether the medication or treatment was ongoing. Concomitant medications will be coded by using WHO Drug Dictionary version September 2012.

11. Efficacy Endpoints

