The best response (CR, PR, SD or PD according to RECIST 1.1 and according to Choi criteria) for each patient with measurable disease who received at least one dose of study drug will be listed by cohort and response rate (CR or PR) between the two arms will be compared using Pearson's chi-square test or Fisher's exact test. Stable disease will be defined as lack of tumor progression lasting for 2 cycles or longer. Additional analysis will be conducted based on duration of response, defined from the time to first response (CR or PR) to disease progression and will be compared between arms using Kaplan Meier methods. Other secondary analysis would include disease stability rate (DSR) defined as the percent of subjects in ITT population with CR, PR and SD at 16 weeks, and will be compared using Pearson's chi-square test or Fisher's exact test.

The primary Phase 2 endpoint of PFS will be determined based on objective tumor assessments made by Central Radiographic Review according to RECIST version 1.1. PFS will also be determined based on investigator assessment. Treatment decisions will be made by the investigator based on application of RECIST 1.1. Supportive analyses will be performed based on investigator assessments of disease response and progression. In cases where Central Radiographic Review assessment of response conflict with investigator assessment the data will be censored as it related to the endpoint.

The clinical response of the study treatment will be assessed by a comparative evaluation of computed tomography (CT) or magnetic resonance imaging (MRI) scans prior to enrollment into the study and every 8 weeks using RECIST 1.1 (primary endpoint) or Choi criteria (secondary endpoint).

A listing will be provided for best overall response, i.e., CR, PR, SD, PD or NA (not assessable due to missing or incomplete assessments or inconsistent assessment methods) for each patient. A listing or figure will also be provided for duration of PFS and sum of the diameters for target lesions over time in patients. The listings for best overall response and PFS will compare to overall response and PFS of treatments received prior to study entry, including the most recent treatment that included a VEGF inhibitor.

12. Safety Analyses

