16.2.8 Individual Laboratory Measurements by Patient

- Listing 16.2.8.1 Abnormal Laboratory Results – Hematology
- Listing 16.2.8.2 Abnormal Laboratory Results – Coagulation
- Listing 16.2.8.3 Abnormal Laboratory Results – Chemistry
- Listing 16.2.8.4 Abnormal Laboratory Results – Urinalysis
- 16.2.8.5 Final Immunogenicity Report
- 16.2.9 Other
 - Listing 16.2.9.1 Vital Signs
 - Listing 16.2.9.2 Abnormal and Clinically Significant Physical Exam Results
 - Listing 16.2.9.3 ECG Results
 - Listing 16.2.9.4 ECOG Performance Status
 - Listing 16.2.9.5 Pregnancy at Screening
 - Listing 16.2.9.6 Archival Tumor Specimen
 - Listing 16.2.9.7 Drug allergies
 - Listing 16.2.9.8 Protein Biomarkers

20.2. Appended Listings Phase 2:

- 16.1 Study Information
 - Listing 16.1.1 Listing of Informed Consent and Reconsent
 - Listing 16.1.3 Listing of IRBs and Sample Consent Forms
 - Listing 16.1.4 Listing of Investigators and Other Important Participants in the Study
 - Listing 16.1.5 Signature of Sponsor’s Responsible Medical Officer
 - Listing 16.1.6 Listing of Patients receiving test drug from specific batches
 - Listing 16.1.9 Documentation of Statistical Methods
 - Listing 16.1.11 Publications Based on the Study
 - Listing 16.1.12 Important Publications Referenced in the Report
- 16.2 Patient Data Listings
 - Listing 16.2.1 Discontinued Patients
 - Listing 16.2.2 Table of Protocol Deviations
 - Listing 16.2.2.1 Inclusion Exclusion
 - Listing 16.2.3 Patients excluded from Efficacy Analysis
 - 16.2.4 Demographic Data
 - Listing 16.2.4.1 Demographics
 - Listing 16.2.4.2 Disease Present at Screening
 - Listing 16.2.4.3 Primary Diagnosis
 - Listing 16.2.4.4 Prior Cancer Therapy
 - Listing 16.2.4.5 Time to tumor progression on most recent VEGF inhibitor therapy
 - Listing 16.2.4.6 Prior Cancer Surgery
 - Listing 16.2.4.7 Prior Cancer Radiation Therapy
 - Listing 16.2.4.8 Medical History and Baseline Emergent Adverse Events
 - Listing 16.2.4.9 Concomitant Medications
 - Listing 16.2.4.10 Concomitant Treatments
 - Listing 16.2.4.11 TRC105 Pre-Medications
 - 16.2.5 Compliance and/or Drug Concentration Data
 - Listing 16.2.5.1 TRC105 Dosing Record
 - Listing 16.2.5.2 Axitinib Dosing Record
 - 16.2.5.3 Final PK Report
 - 16.2.6 Individual Efficacy Response Data

- Listing 16.2.6.1 Overall Tumor Assessment
- Listing 16.2.6.2 Duration of RECIST Response (PR/CR)
- Listing 16.2.6.3 Time to Tumor Progression or Death
- Listing 16.2.6.4 Target Lesions

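### Partial prior-therapy dates are imputed to give the longest possible prior time to progression, with no cap at study entry; only the descriptive prior-versus-on-study listings are affected

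*SAP*

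**What the plan says.** SAP Section 7 (Missing Data) makes its table binding for incomplete dates: "Partial dates will be imputed according to the following table". It adds that "CRFs that are not listed below are not expected to contain partial dates". The rows that matter here are "Prior Cancer Therapy Start Date First of Month Jan 01 of Year" and, for the field "Date of Progression on Therapy" on the same form, "Date of Progression on Therapy Last day of Month Dec 31 of Year". A partial stop date is also moved to the end of the month or year. The section states no upper limit, ordering check or flag for imputed values.

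These dates are then used. SAP Section 11.1 states that "The listings for best overall response and PFS will compare to overall response and PFS of treatments received prior to study entry", and names the most recent VEGF-inhibitor treatment among them. Listing 16.2.4.5, planned for Phase 1b (SAP 20.1) and Phase 2 (SAP 20.2), is titled "Time to tumor progression on most recent VEGF inhibitor therapy".

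On-study PFS in Phase 2 runs from randomisation to progression or death (SAP 11.1). The table has no row for randomisation, tumour assessment or death, so that duration uses recorded dates.

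**The concern.** First-of-period starts and end-of-period stops suit adverse events and concomitant medications, where the aim is not to miss an overlap with treatment. They suit a duration badly. Here the start moves to its earliest possible value and the progression to its latest, so both errors lengthen the interval and neither can offset the other. On-study PFS in Phase 2 gets no matching stretch. A reader who sets one beside the other sees prior treatment as having held the disease longer than it did, most of all in patients with the poorest outside records.

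The missing cap is a separate fault. Phase 2 patients must have progressed on a prior VEGF inhibitor to be eligible (Protocol 5.1.1, criterion 1). A listing that dates this progression after randomisation contradicts the patient's own entry into the trial.

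**Working it through.** The plan states no figure for the effect of this rule, so there is none to reproduce. The check is calendar arithmetic, assuming the true date is uniform within the unknown period. It was confirmed by simulating 400,000 prior-therapy intervals (starts uniform over 2012–2015, exponential durations with medians of 3.4, 4.8, 8.5 and 11 months).

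**1. Month known, day missing.** In a month of L days, moving the date to one end shifts it by (L − 1)/2 days on average. The day-weighted month length in a 365-day year is (7 × 31² + 4 × 30² + 28²)/365 = 11,111/365 = 30.44.
- One partial date: (30.44 − 1)/2 = 14.7 days, range 0 to 30.
- Both partial: 2 × 14.72 = 29.4 days, range 0 to 60. The simulation gave 29.4 to 29.5 days (0.97 month), whatever the true median.

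**2. Only the year known.**
- One partial date: (365 − 1)/2 = 182 days, range 0 to 365.
- Both partial: 364 days, range 0 to 730.

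**3. Example.** Start March 2015, progression August 2015. The true interval lies between 123 days (31 March to 1 August) and 183 days (1 March to 31 August). The rule always returns 183. With year-only dates, any drug started and failed within one non-leap year is listed as 364 days.

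**4. Average over all patients.** This is the affected share times the values above. The documents give no share, so these are assumptions:

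| Share with both dates partial | Month-only | Year-only |
|---|---|---|
| 10% | 2.9 days | 36 days |
| 25% | 7.4 days | 91 days |
| 50% | 14.7 days | 182 days |

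**5. Scale.** The stretched quantity is PFS on the earlier drug. Protocol Table 3 gives 11 months for first-line sunitinib and 8.5 months for bevacizumab plus interferon. On those, 0.97 month is 0.97/11 = 9% and 0.97/8.5 = 11%.

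**6. Dates after randomisation.** Protocol 5.1.2, exclusion 5, admits patients less than 28 days after prior therapy once five half-lives have passed, so progression and randomisation can share a month. For instance, a progression on 3 June with the day missing becomes 30 June. If the patient was randomised on 24 June, the listed progression is 6 days too late to be possible. With a year-only date, 31 December falls after any earlier randomisation in that year.

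**7. Midpoint alternatives.**
- *15th of the month, both dates month-only:* mean error about 0 days, SD about 12 days, range −30 to +30.
- *Mid-year, both dates year-only:* mean error about 0, but SD 142 to 148 days. Two dates in the same year also give exactly 0 days. With uniform starts and an exponential duration of median m months, that share is 1 − (1 − e^(−a))/a, where a = 12 ln 2/m. For m = 11, a = 0.756 and the share is 0.298; for m = 4.8, a = 1.733 and the share is 0.525.

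**The case against.** The strongest reply is that nothing inferential depends on these dates, and that is correct. The SAP plans listings only, with no test, ratio or summary estimate of prior against on-study PFS. A reader might infer that the trial's treatment comparison is biased. It is not: the primary analysis is a stratified log-rank test between arms that uses no prior-therapy date, and the rule applies equally to both arms. Nor does the rule flatter the product, since a longer prior PFS makes study treatment look worse.

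Three further stronger readings fail:

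- *That the SAP expects many partial dates on this form.* It says only that unlisted forms should have none; the converse does not follow. Informed Consent is also listed, where partial dates are hardly likely. Year-only dates for the latest VEGF inhibitor look improbable too, because eligibility turns on month-level and 28-day windows.
- *That prior PFS is stretched by a month or a year in general.* Those means apply to a patient with both dates partial at that level, and halve when one is partial.
- *That the stretch is a fifth of PFS.* This sets 0.97 month against the SAP's 4.8 months, but that figure is the expected result on axitinib: "The expected PFS of patients treated with axitinib who have progressed following first line treatment with a VEGFR TKI is 4.8 months". It is not PFS on the earlier drug.

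First-and-last imputation is also the table's convention for every start and stop pair, and listing all collected data should let a careful reader find incomplete dates. That softens the point but does not remove it. The same table already uses a midpoint for birth date, and no convention justifies a progression dated after study entry.

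**Conclusion.** The point holds in a limited form and is minor. Wherever a prior-therapy start or progression date is partial, the error in the listed prior duration is never negative, with the means in steps 1 and 2. The sizes rest on true dates being uniform within the unknown period and do not depend on the true prior PFS. The study-wide effect cannot be fixed without the share of partial dates. If a quarter of patients had both dates month-only, it would be about 7 days.

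The consequence is confined to the descriptive comparison in SAP 11.1 and to Listing 16.2.4.5. It may matter somewhat more in Phase 1b, which has no randomised control to set beside prior PFS. The possibility of a progression dated after randomisation follows directly from the rule, though how often it would occur is unknown.

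**What to change.** In SAP Section 7, for Prior Cancer Therapy only:

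1. Where month and year are known, impute the 15th for start, stop and progression dates.
2. Require start ≤ progression ≤ randomisation (Phase 2) or first dose (Phase 1b), truncating an imputed date to any known bound.
3. Flag every imputed duration in the listings.
4. Where either date is year-only, do not impute a mid-year date for the duration. Show the minimum–maximum range, or list it as not determinable.

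Item 4 is needed because mid-year imputation would replace an overlong prior PFS with many zeros (step 7). A start and progression in the same month would likewise give 0 days under item 1. The flag covers this, and the range can be shown instead.

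The cost is a few table entries, one ordering rule and a flag, with no new data. The downside is that some year-only prior PFS values will no longer appear as single numbers.
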